4.1. Overall Design

This is a multicenter, open label study assessing the interictal impact of erenumab-aooe in participants with migraine. The study population will consist of 54 participants 18 to 65 years old, with at least 4 and up to 20 migraine days per month (inclusive) following ICHD-III criteria for migraine with or without aura.

At Visit 1, the participant will sign the informed consent indicating they are willing to participate in the study and will provide basic demographic information, have a comprehensive review of their medical history and prior and concomitant medications. A physical and neurological examination (including vital signs) will be performed as well as a 12-lead Electrocardiography (ECG), screening CMP labs, and the PHQ-9 will be completed. Women of childbearing potential (WOCB) will complete a urine pregnancy test. All participants will complete the MFIQ questionnaire. Inclusion and Exclusion criteria will also be reviewed. Participants who meet the study criteria will be dispensed the activity tracker and its associated phone application instructions, as well as their unique Daily Headache Diary (DHD) URL and its instructions. Participants will then enter into a 28-day run-in period. During the 28-day run-in period, all participants will be monitored through the use of electronic Daily Headache Diary (DHD) to ensure they continue to meet all inclusion criteria, and none of the exclusion criteria. During this run-in period, participants will continue treating their migraines and other defined conditions with their usual treatment providing it has been stable for a minimum of 3 months. Daily electronic diaries will be used to assess symptoms and treatment response throughout the run-in period.

Visit 2 will take place 28 to 33 days following Visit 1. Those participants who (1) continue to meet eligibility criteria (2) experienced 4-20 migraine days that meet ICHD-III criteria for migraine and (3) have completed at least 23/28 diary days will be eligible to be enrolled into the study. At this visit a physical examination (including vital signs) will be performed, WOCB will complete a urine pregnancy test, and all participants will complete the PHQ-9. Medical history and/or adverse events and concomitant medications will be reviewed and updated as needed. Participant's DHD will be reviewed for compliance, and participants will complete the following questionnaires:

- MFIQ
- MIBS-4
- WPAI-M

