#### 4.3.4. Change in Migraine Days from Baseline to Each 4-Week Treatment Period

##### 4.3.4.1. Definition of Endpoint

Headache and Migraine data will be recorded by the participants into an electronic daily headache diary (DHD) throughout the study. The DHDs are web-based and can be completed on any internet enabled device using the participant's unique log in credentials. Site personnel will be responsible for instructing participants on the requirement for timely and daily completion of the DHD.

Clinic visits are to occur every 28 days throughout the study; however, in practice, there may or may not be an exact 28-day duration between two consecutive visits. As such, participants may have more or less than 28 diary entries between two consecutive visits. To account for this, the following will be utilized:

- **Baseline:** eDiary information entered during the *last* 28 continuous days of the run-in period will serve as the “baseline” for calculating change from baseline. For example, if a participant's run-in period is 31 days long, and the participant entered eDiary information for all 31 days, the last 28 days (leading up to first drug administration) will be used to calculate and derive endpoint variables, with the first three eDiary entries (days 1, 2, and 3) being discarded from the analysis datasets.
- **Treatment Months:** If a participant enters more than 28 days of eDiary information between clinic visits during the treatment phase of the study, the *first* 28 continuous day's eDiary entries for each period/month will be used for analyses. For example, if a participant has a duration of 31 days between Visit 2 and Visit 3, and the participant entered eDiary information for all 31 days, the first 28 days (following Visit 2) of eDiary information will be used to calculate and derive endpoint variables, with the last three eDiary entries (days 29, 30, and 31) being discarded from the analysis datasets.

Migraine headache days are defined in this study as an attack within a calendar day (00:00 to 23:59) that meet at least one of the two following criteria:

1. A headache attack that includes all of the following criteria:

This document, including any source code, is the property of [Clinvest Research LLC](#), and may contain proprietary, confidential, or legally privileged information. No part of this report, or any information contained therein, may be disseminated without the written consent of [Clinvest Research LLC](#).

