A. Headache attacks lasting 4-72 hours (untreated or unsuccessfully treated)

B. Headache has at least two of the following four characteristics:

1. unilateral location
2. pulsating quality
3. moderate or severe pain intensity
4. aggravation by or causing avoidance of routine physical activity (e.g., walking or climbing stairs)

C. During headache at least one of the following:

1. nausea and/or vomiting
2. photophobia and phonophobia

2. A headache attack of any duration with relief (defined as a “Yes” answer to the eDiary question “*Did you get relief from taking the above medication(s) yesterday?*” [HD\_RLFYN]) from the following migraine-specific acute medication(s):

- Advil (Ibuprofen)
- Aleve (Naproxen)
- Amerge (Naratriptan)
- Axert (Almotriptan)
- Butabitol
- Cafergot (Ergotamine Tartrate/Caffeine)
- Cambia (Diclofenac Potassium)
- Cefaly
- DHE 45 (Dihydroergotamine)
- Ergomar (Ergotamine Tartrate Sublingual Tablets)
- Excedrin Migraine
- Fioricet
- Fiorinal
- Frova (Frovatriptan)
- gammaCore Sapphire
- Imitrex (Sumatriptan)
- Indocin (Indomethacin)
- Maxalt (Rizatriptan)
- Midrin (Isometheptene Mucate, Dichloralphenazone and Acetaminophen)
- Migerot (Ergotamine Tartrate/Caffeine Suppository)
- Migranol
- Migril (Ergotamine, Cylizine, and Caffeine)
- Namenda (memantine)
- Onzetta (Sumatriptan Nasal Powder)
- Prednisone

This document, including any source code, is the property of [Clinvest Research LLC](#), and may contain proprietary, confidential, or legally privileged information. No part of this report, or any information contained therein, may be disseminated without the written consent of [Clinvest Research LLC](#).

- Relpax (Electriptan)
- Reyvow (Lasmiditan)
- Sumavel (Sumatriptan Needleless Injection)
- Tivorbex (Indomethacin)
- Treximet (Sumatriptan/Naproxen)
- Tylenol (Acetaminophen)
- Zembrace (Sumatriptan injection)
- Zomig (Zolmitriptan)
- Zorvolex (Diclofenac)

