#### **4.3.4.2. Main Analytical Approach**

Only data from those participants who meet criteria for the Full Analysis set will be analyzed. Participants will be asked to record diary data each day for the previous day (24-hour period). If a participant does not experience a headache in the previous 24-hour period, the diary must still be completed as instructed. Participant's diaries may vary day to day based on their responses. All participants should have at least 80% compliance with diary completion throughout the length of the study. Participants will record headache severity, symptoms, use of acute medications, as well as additional assessments as required.

This frequency of migraine days will be derived from the participants' eDiary entries. The eDiary entries are based on the count of days with migraine headaches for each 28-day time points (baseline, treatment month 1, treatment month 2, treatment month 3). Participants with less than 80% diary compliance for any study period (defined as <23 completed eDiaries during that study period/month) will be considered Missing Data for that entire study period/month. The number of migraine days for these study periods/months will be imputed using the LOCF method. Data for this secondary endpoint will be analyzed via a repeated measures ANOVA comparing participant's mean change in the number of migraine days from baseline to each of the 4-week treatment periods. Significant changes will be followed up using within groups, repeated measures *t*-tests as needed.

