#### Diagnostic criteria:

- A. At least five attacks fulfilling criteria B–D
- B. Headache attacks lasting 4–72 hours (when untreated or unsuccessfully treated)
- C. Headache has at least two of the following four characteristics:
  - 1. unilateral location
  - 2. pulsating quality
  - 3. moderate or severe pain intensity
  - 4. aggravation by or causing avoidance of routine physical activity (e.g. walking or climbing stairs)
- D. During headache at least one of the following:
  - 1. nausea and/or vomiting
  - 2. photophobia and phonophobia
- E. Not better accounted for by another ICHD-3 diagnosis.

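### SAP 4.3.4.1, criterion 2: relief from a listed product alone makes a migraine day, and the list is wider than its migraine-specific label, so an allowed tension-type headache can be counted

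*SAP*

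**What the plan says.** SAP 4.3.4.1 counts a calendar day as a migraine day when it holds an attack "that meet at least one of the two following criteria". Criterion 1 asks for a duration of 4 to 72 hours, at least two of four pain characteristics (item B), and nausea or vomiting, or sensitivity to both light and sound (item C).

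Criterion 2 is "A headache attack of any duration with relief". Relief means a Yes to one diary item, "Did you get relief from taking the above medication(s) yesterday", and it must come "from the following migraine-specific acute medication(s" list that follows. The list has 34 entries, among them "Tylenol (Acetaminophen", ibuprofen, prednisone and memantine.

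SAP 4.3.4.2 analyses the "mean change in the number of migraine days from baseline to each of the 4-week treatment periods" by repeated measures ANOVA. Protocol 5.1 permits other primary headaches and gives tension-type headache as its example (no. 8). It also treats migraine days and total headache days as separate counts (no. 6). Protocol 4.1, repeated in SAP 1.2, describes those eligible at Visit 2 as having "experienced 4-20 migraine days that meet ICHD-III criteria for migraine". The ICHD-III criteria reproduced in SAP 6.2 and Protocol 10.5 include the item "Not better accounted for by another ICHD-3 diagnosis". The day definition does not carry that item over.

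**The concern.** Counting a treated attack on the strength of relief is reasonable when the product itself points to migraine. It is much weaker evidence when the product is a general analgesic. Under criterion 2 a short, featureless headache that responds to acetaminophen counts the same as a full migraine.

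The population makes this possible in practice. Tension-type headache is allowed, and Protocol 5.2 no. 12 admits medication overuse headache with drugs other than opioids or butalbital, so frequent users of simple analgesics can enroll.

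What is at stake is the meaning of the migraine-day counts. If non-migraine headaches or analgesic habits change during treatment, the change from baseline is also affected. With one open-label arm (Protocol 6.3) there is no control group in which the same shift would appear.

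**Working it through.** The plan states no figure on this point, so the check is a count, a logical trace and an illustration.

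**Step 1. Sort the list by the ingredients the SAP prints.**

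| Group | Entries | Number |
|---|---|---|
| Triptan (11), ergot (5), lasmiditan (1) | Amerge, Axert, Frova, Imitrex, Maxalt, Onzetta, Relpax, Sumavel, Treximet, Zembrace, Zomig; Cafergot, DHE 45, Ergomar, Migerot, Migril; Reyvow | 17 |
| Other named ingredient | Advil, Aleve, Cambia, Zorvolex, Indocin, Tivorbex, Tylenol, Prednisone, Namenda | 9 |
| Combination naming none of the three classes | Midrin | 1 |
| No ingredient printed | Butabitol, Cefaly, Excedrin Migraine, Fioricet, Fiorinal, gammaCore Sapphire, Migranol | 7 |

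17 + 9 + 1 + 7 = 34. From the printed text, the entries outside the three classes number at least 9 + 1 = 10 and at most 10 + 7 = 17. Leaving Midrin aside, the floor is 9.

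**Step 2. Trace one headache.** Take a one-hour tension-type headache with none of the features in B or C, relieved by acetaminophen. Criterion 1 fails on duration, B and C. Criterion 2 is met. Either criterion is enough, so the day counts. Nothing in SAP 4.3.4 removes it. Protocol 5.1 no. 8 tests whether the participant can tell headache types apart, but the derivation does not use that judgement.

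**Step 3. Illustrate the level (all inputs assumed).** Per 28 days at baseline: M = 8 criterion-1 days; E = 2 migraines stopped early and relieved by a listed triptan; O = 2 to 8 separate days with other headaches, of which a share q = 0.25 to 1 is relieved by a listed product outside the three classes. True level = M + E = 10. Level under the SAP = 10 + O × q. Criterion 1 alone reads 8.

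**Step 4. Illustrate the change.** Let migraine fall by 40%: true change = 0.6 × 10 − 10 = −4.0.

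| O | q | SAP baseline | (a) O and q constant | (b) O halved: −4.0 − 0.5 × O × q |
|---|---|---|---|---|
| 2 | 0.25 | 10.5 | −4.0 | −4.25 |
| 4 | 0.5 | 12 | −4.0 | −5.0 |
| 8 | 1 | 18 | −4.0 | −8.0 |

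(c) O constant, q rising from 0.25 to 0.5: change = −4.0 + 0.25 × O = −3.5, −3.0 and −2.0 for O = 2, 4 and 8.

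Criterion 1 alone: 0.6 × 8 − 8 = −3.2.

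**Step 5. Test a restricted count on the same inputs.** Let relief alone qualify only for the 17 class entries. With no switch of product, the change is −4.0. If the remaining 0.6 × 2 = 1.2 early-stopped migraines move from a triptan to an NSAID with no features recorded, it reads 0.6 × 8 − 10 = −5.2. With the reverse switch it reads 0.6 × 10 − 8 = −2.0.

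**The case against.** **A rule for treated attacks is needed.** Criterion 1 covers attacks that were untreated or not successfully treated, so criterion 1 alone undercounts (8 against 10 above). This stands. Criterion 2 should be narrowed, not removed.

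**The class boundary is not the SAP's.** The documents do not define migraine-specific as triptans, ergots and lasmiditan. That is true, and the boundary is a reading. The underlying problem is the missing feature requirement, and drug class matters because the label is the only thing that could justify relief standing in for features.

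**The missing ICHD-III exclusion item proves little.** It is a diagnostic judgement made at entry, and the five-attack item is not carried into the day definition either. Agreed. The point rests on criterion 2 itself.

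**Aura.** Migraine with aura is eligible, and its ICHD-III criteria (Protocol 10.5, SAP 6.2.2) require neither the 4-hour duration nor B and C. A relieved aura attack may therefore enter only through criterion 2. This stands, and it has two consequences. A repair that required only B and C would lose such attacks. And a reader might subtract the 4 entry migraine days from the cap of 20 headache days and infer that at most 16 baseline days can come through criterion 2 alone. The documents do not support that ceiling, because the 4 entry days need not meet criterion 1.

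**No bias in the change is shown.** Correct. A reader might infer that the migraine-day reduction will be overstated. The documents give no rate of relieved non-migraine headaches and no reason to expect one direction.

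**A restricted count is not proven better.** In Step 5 a product switch gives an error as large as the worst of case (c). This is why timing and sensitivity analyses matter in the repair.

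**Conclusion.** The point holds as a misclassification written into the rule. Criterion 2 scores an allowed non-migraine headache as a migraine day when a listed general product relieves it, and 9 to 10 of the 34 entries (up to 17, depending on the seven with no printed ingredient) fall outside the three classes that the label suggests.

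The level can be inflated at baseline and on treatment. The change from baseline is unaffected if other headaches, their treatment and their relief are constant. Otherwise it can shift either way. The range of −8.0 to −2.0 around a true −4.0 shows the mechanism under assumed inputs and is not an estimate.

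Only this secondary endpoint is touched. The primary endpoint (MFIQ item 16) and N = 54 do not depend on it. The enrollment count is described by ICHD-III criteria and the analysis baseline by the SAP rule, so the two can differ for the same diary. A reader might infer that ineligible participants were enrolled, but nothing in the documents shows that.

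**What to change.** 1. Correct the migraine-specific label. State the group of each of the 34 entries, including the seven without an ingredient, and give one rule for days with products from both groups.
2. Derive a restricted count for the analysis baseline and every treatment month, without reopening enrollment. Relief alone qualifies for the listed triptans (and combinations), ergots and lasmiditan. Relief from any other entry also requires B and C of criterion 1, with the 4-hour duration waived, or recorded aura.
3. First confirm that the diary holds these items on treated days. Protocol 8.1.3 lists severity, symptoms and acute medication, but the form is not in the documents and its content may vary by day.
4. Make the restricted count the main definition only if it is fixed before anyone reviews treatment-period diary data. In an open-label study, database lock is too late a cut-off, and SAP 4.4.2.1 already speaks of questionnaires in the past tense. Otherwise keep the stated definition as main and report the restricted-list and criterion-1-only counts as sensitivity analyses, labelled post hoc if data have been seen.

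The cost is SAP wording and re-derivation of one variable. The downsides should be stated in the SAP:
- Migraines stopped early with another product before features appear are not counted.
- A switch of product class can move the count (Step 5).
- One relief item cannot attribute relief among several products.
- A tension-type headache relieved by a triptan would still count.

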#### **4.3.4.2. Main Analytical Approach**

Only data from those participants who meet criteria for the Full Analysis set will be analyzed. Participants will be asked to record diary data each day for the previous day (24-hour period). If a participant does not experience a headache in the previous 24-hour period, the diary must still be completed as instructed. Participant's diaries may vary day to day based on their responses. All participants should have at least 80% compliance with diary completion throughout the length of the study. Participants will record headache severity, symptoms, use of acute medications, as well as additional assessments as required.

This frequency of migraine days will be derived from the participants' eDiary entries. The eDiary entries are based on the count of days with migraine headaches for each 28-day time points (baseline, treatment month 1, treatment month 2, treatment month 3). Participants with less than 80% diary compliance for any study period (defined as <23 completed eDiaries during that study period/month) will be considered Missing Data for that entire study period/month. The number of migraine days for these study periods/months will be imputed using the LOCF method. Data for this secondary endpoint will be analyzed via a repeated measures ANOVA comparing participant's mean change in the number of migraine days from baseline to each of the 4-week treatment periods. Significant changes will be followed up using within groups, repeated measures *t*-tests as needed.

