5.1. Inclusion Criteria

Participants are eligible to be included in the study only if all of the following criteria apply:

1. willing to participate and sign informed consent;
2. ability to understand informed consent and study procedures, including able to use the electronic Daily Headache Diary;
3. in good general health based on investigator's judgment;
4. must be between 18 to 65 years of age, inclusive, at time of Visit 2;
5. have migraine with or without aura meeting the diagnostic criteria listed in the International Classification of Headache Disorders 3rd edition (ICHD-III; Appendix 5);
6. verification of headache frequency through prospectively collected baseline information during the 28-day screening/baseline phase reporting 4-20 migraine days and no more than 20 total headache days;
7. onset of migraine before age 50;
8. able to differentiate migraine from other primary headache types allowed in the study (e.g., tension-type headache);
9. stable history of migraine at least 3 months prior to screening with headache free periods;
10. not currently taking a migraine preventive OR has been taking a stable dose of a preventive for at least 90 days prior to screening and agrees to not start, stop, or change medication and/or dosage during the study period;
* * participants on migraine preventive should have stable headache pattern
11. Must answer "Moderately", "Very Much", or "Extremely" to Item 16 (*In the past 7 days, overall, how much did a migraine affect your usual activities?*) on the Migraine Functional Impact Questionnaire (MFIQ) at screening;
12. women may be included only if they have a negative pregnancy test at screening and baseline, are sterile, or postmenopausal. Women of childbearing potential (WOCBP) whose male partners are potentially fertile (i.e., no vasectomy) must use highly effective birth control methods for the duration of the study (i.e., starting at screening). Definitions of WOCBP, sterile and postmenopausal women, male contraception, and highly effective

and acceptable birth control methods are to be determined based on investigator's judgment;

13. demonstrated compliance with the electronic Daily Headache Diary during the 28-day screening/baseline phase as defined by entry of headache data on a minimum of 23 days;
14. is willing to wear activity/sleep tracker throughout the duration of the trial;
15. has a smartphone and willing to install activity tracker app on phone.

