## Version History

This statistical analysis plan (SAP) for Study 19-001AM is based on the protocol dated 16-Sep-2020.

SAP Version	Date	Change	Rationale
1	13-Oct-2021	Not applicable	Original version
2	23-Mar-2022	Revised Section 4.1.1 Missing Data	Clarification of how to handle missing data

This document, including any source code, is the property of [Clinvest Research LLC](#), and may contain proprietary, confidential, or legally privileged information. No part of this report, or any information contained therein, may be disseminated without the written consent of [Clinvest Research LLC](#).

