Visit 2 will take place 28 to 33 days following Visit 1. Those participants who (1) continue to meet eligibility criteria (2) experienced 4-20 migraine days that meet ICHD-III criteria for migraine and (3) have completed at least 23/28 diary days will be eligible to be enrolled into the study. At this visit a physical examination (including vital signs) will be performed, WOCB will complete a urine pregnancy test, and all participants will complete the PHQ-9. Medical history and/or adverse events and concomitant medications will be reviewed and updated as needed. Participant's DHD will be reviewed for compliance, and participants will complete the following questionnaires:

- MFIQ
- MIBS-4
- WPAI-M
- SDSF
- GSE-SF
- BMWS
- FAMS

Finally, all eligible participants will receive an injection of 140 mg erenumab-aooe. Participants will continue completing diary headache diaries for the remainder of the trial.

Visits 3-5 will take place on days 29 (+/-3d), 57 (+/-3d), and 85 (+/-3d), following Visit 2. At each visit: a physical examination (including vital signs) will be performed, WOCB will complete a urine pregnancy test, and all participants will complete the PHQ-9. Medical history

This document, including any source code, is the property of [Clinvest Research LLC](#), and may contain proprietary, confidential, or legally privileged information. No part of this report, or any information contained therein, may be disseminated without the written consent of [Clinvest Research LLC](#).

and/or adverse events and concomitant medications will be reviewed and updated as needed. Participant's DHD will be reviewed for compliance, and participants will complete the following questionnaires:

- MFIQ
- MIBS-4
- WPAI-M
- SDSF
- GSE-SF
- BMWS
- FAMS

Finally, all eligible participants will receive an injection of 140 mg erenumab-aooe. Visit 5 (End of Study) will not include injections but will include comprehensive metabolic panel (CMP) laboratory.

This document, including any source code, is the property of [Clinvest Research LLC](#), and may contain proprietary, confidential, or legally privileged information. No part of this report, or any information contained therein, may be disseminated without the written consent of [Clinvest Research LLC](#).

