#### 4.1.1. Missing Data

Missing data for full analysis population participants will be imputed as follows:

- Missing values on questionnaire items will be handled according to the questionnaire's scoring manual. When no guidance is specified in a questionnaire scoring manual, missing items will be left null and the score and/or sub-score will be imputed using a last observation carried forward (LOCF) method. This type of imputation replaces the missing value with the last observation value obtained for the participant.
- Missing DHD entries (Monthly Migraine Days) will be imputed as follows:
  - < 14 DHDs completed: Participant's average MMDs for that study period will be replaced with their last study period's MMD using the LOCF method.
  - $\geq 14$  DHDs completed: Participant's average MMDs for that study period will be imputed based on the data available in that study period and prorated to 28 days.
- Missing Garmin data (Steps and Sleep) will be imputed as follows:
  - < 14 days synced: Participant's average steps and/or sleep for that study period will be replaced with their last study period's steps and/or sleep using the LOCF method.
  - $\geq 14$  days synced: Participant's steps and/or sleep for the missing day will be imputed using the participant's mean steps and/or sleep for the data available in that study period.

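### For treatment months with 14–22 completed diaries, the SAP prescribes two different migraine-day values: proration in 4.1.1 and LOCF in 4.3.4.2

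*SAP*

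**What the plan says.** SAP 4.1.1 (Missing Data) sets a rule specifically for missing diary entries behind monthly migraine days, with its cut at 14 completed diaries. Below 14: "Participant's average MMDs for that study period will be replaced with their last study period's MMD using the LOCF method". At 14 or more: "Participant's average MMDs for that study period will be imputed based on the data available in that study period and prorated to 28 days".

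SAP 4.3.4.2, the analysis section for the migraine-day endpoint, puts the cut at 23: "Participants with less than 80% diary compliance for any study period (defined as <23 completed eDiaries during that study period/month) will be considered Missing Data". It applies this to the whole period and continues: "The number of migraine days for these study periods/months will be imputed using the LOCF method".

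Neither section refers to the other. The Version History lists only Section 4.1.1 as revised in version 2, with the rationale "Clarification of how to handle missing data". Protocol 9.4.1 names LOCF where appropriate and gives no diary threshold for imputation. SAP 4.8 declares no changes from the protocol-planned analyses.

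**The concern.** Both rules concern the same variable over the same 28-day periods. A programmer who follows 4.1.1 uses the recorded days of a month with, say, 20 diaries. One who follows 4.3.4.2 discards them and carries the previous month's value. The two derived values can differ by several migraine days for one participant, in either direction.

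Month 1 is the clearest case. The only earlier period is baseline, so LOCF sets the change from baseline to exactly 0, although up to 22 days were observed.

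If the text is not settled before database lock, the choice of rule could be made in an open-label study with the data in view. Nothing in the documents says that this happened.

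**Working it through.** **Threshold.** 0.80 × 28 = 22.4, so the smallest compliant count is 23 (23/28 = 82.1%; 22/28 = 78.6%). The SAP's <23 cut is reproduced.

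**Where the rules disagree**, comparing every count from 0 to 28:

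| Completed diaries | SAP 4.1.1 | SAP 4.3.4.2 |
|---|---|---|
| 0–13 | LOCF | LOCF |
| 14–22 | prorate to 28 | LOCF |
| 23–28 | observed data | observed data |

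The method differs at exactly the nine counts 14 to 22.

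**Effect on one record (assumed data, previous period 10 migraine days).** Prorated value = migraine days × 28 / completed diaries.
- 3 migraine days in 20 diaries: 3 × 28/20 = 4.2, against 10 by LOCF.
- 8 migraine days in 20 diaries: 8 × 28/20 = 11.2, against 10 by LOCF.

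**Carry-over.** Below 14 diaries both sections use LOCF, but the value carried can differ. Suppose month 1 is complete at 8 migraine days, month 2 has 3 migraine days in 18 diaries, and month 3 has 10 diaries. Under 4.1.1, month 2 is 3 × 28/18 = 4.7, and that is carried into month 3. Under 4.3.4.2, month 2 is already carried as 8, and so is month 3.

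**How often.** The documents give no completion rate, so daily completion p is assumed at 95%, 90% and 85%.
- Independent days: P(14 ≤ X ≤ 22) with X ~ Binomial(28, p).
- Clustered misses: each participant's completion probability is drawn from Beta(9p, 9(1 − p)), which gives an intraclass correlation of 1/(9 + 1) = 0.1 (assumed). Enrolled participants have already passed a diary screen (Protocol 5.1, inclusion criterion 13: "as defined by entry of headache data on a minimum of 23 days"). The relevant share is therefore P(14 ≤ X₁ ≤ 22 given X₀ ≥ 23), where X₀ is the run-in count and X₁ a treatment-month count with the same completion probability.

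| Assumed p | Independent days | × 54 | Clustered, given ≥23 of 28 at run-in | × 54 |
|---|---|---|---|---|
| 95% | 0.2% | 0.1 | 2.9% | 1.6 |
| 90% | 5.5% | 3.0 | 7.4% | 4.0 |
| 85% | 23.5% | 12.7 | 13.0% | 7.0 |

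**Precision cost of proration.** With 10 true migraine days in 28 and days missing at random, the added per-participant SD from n diaries is (28/n) × √[n × (10/28) × (18/28) × (28 − n)/27]. This gives 2.6 days at n = 14, 1.9 at 18, 1.6 at 20 and 1.3 at 22.

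**The case against.** The strongest reply is that 4.3.4.2 is the endpoint's own section, so the specific text governs. It is also closer to the protocol, which names only LOCF and asks for 80% diary compliance (Protocol 8.1.3). That does not settle the matter. SAP 4.1.1 is just as specific to migraine days and is the section most recently revised. The clause in Protocol 9.4 that lets the SAP supersede covers differences between protocol and SAP, not conflicts inside the SAP. Nor can the 23-diary sentence be read as a compliance flag only, because the next sentence prescribes how the value is imputed.

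Several stronger readings are tempting, and the documents do not support them:

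- *That the endpoint as a whole cannot be derived.* The value is ambiguous only for participants with a 14–22-diary period, and for later values carried from one. If no such period occurs, the conflict has no effect.
- *That 4.3.4.2 is a proven leftover.* The version history suggests this, but version 1 is not available.
- *That the contradiction shows proration to be right.* It shows only that one rule must be chosen. Proration uses the observed days and avoids a forced 0 in month 1. It also adds noise and assumes that missing days resemble recorded ones.
- *That clustering affects up to 28.3% of months.* Without the run-in screen, the same clustered model gives 6.1%, 16.1% and 28.3%. Enrolled participants have passed that screen, and conditioning on it roughly halves these shares.
- *That baseline is equally exposed.* The natural reading is that eligibility and baseline use the same 28 days, so every enrolled participant has at least 23 baseline diaries. There is one caveat. SAP 1.2 states: "Visit 2 will take place 28 to 33 days following Visit 1", and SAP 4.3.4.1 says the last "28 continuous days of the run-in period will serve as the" baseline. If eligibility were counted on a different 28 days, baseline could fall below 23 diaries, and LOCF would then have nothing to carry. No text says that eligibility is counted that way.

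**Conclusion.** The contradiction stands on the face of the current SAP: in a treatment month with 14–22 completed diaries, one record has two prescribed migraine-day values. In the example they are 4.2 and 10. In month 1, the LOCF rule fixes the change at 0.

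The overall effect cannot be computed, because the documents do not report diary completion. Under the assumed rates, the affected share of participant-months runs from 0.2% to 23.5% with independent days. It runs from 2.9% to 13.0% with clustered misses among screened participants. Both ranges rest on the assumed completion rates, and the second also on the assumed intraclass correlation.

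The problem is confined to one secondary endpoint. The primary analysis of MFIQ item 16 and the sample size of 54 do not use diary counts and are untouched. The point is worth correcting before lock because the text cannot be followed as written, not because it threatens the main conclusion.

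**What to change.** Before database lock, keep one rule and make both sections say it.

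1. Suggested choice: delete the two sentences in SAP 4.3.4.2 that set the <23 cut and the LOCF imputation, and refer to 4.1.1. A period with 14 or more completed diaries is then analysed as migraine days / completed diary days × 28, with LOCF only below 14.
2. Keep 23 of 28 as the eligibility and compliance criterion only.
3. Run the 23-diary LOCF rule as a named sensitivity analysis.
4. State which value is carried forward when the previous period was itself imputed.
5. State that diary eligibility is counted on the same 28 days as the baseline window, or give a rule for a baseline below 23 diaries.

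If the sponsor prefers the 23-diary LOCF rule, change 4.1.1 to match; items 4 and 5 still apply.

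The cost is SAP wording and one line of derivation code, with no new data. The downside of the suggested choice is the added per-participant SD of about 1.3 to 2.6 days in affected months, together with the assumption that unrecorded days resemble recorded ones. The sensitivity analysis would show whether the choice of rule matters.
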